8.1. Photography Procedures

- ## 1. NIKON D7200

Standard, close up and cross-polarized photography of the face will be utilized for evaluation of pigmentation.

- ## 2. Vectra H2 3D Imaging System

Subjects will be instructed to adopt neutral, non-smiling expressions for each photograph.

- ### 3. VISIA Imaging System

Subjects will be instructed to adopt neutral, non-smiling expressions with their eyes gently closed for each photograph. [REDACTED]

[REDACTED]

[REDACTED]

[REDACTED]

8.2 Physician's Global Assessment

Trained clinician reviewers will use the Physician's Global Assessment Scale to evaluate subject's clinical photography and assess melasma response to f1927 laser treatment. [REDACTED]

[REDACTED]

Table 1. Physician's global assessment

Score	Description
0	Clear, except for possible residual discoloration
1	Almost clear, very significant clearance (c. 90%); only minor evidence of hyperpigmentation remains
2	Marked improvement, significant improvement (c. 75%); some disease evidence of hyperpigmentation remains
3	Moderate improvement, intermediate between slight and marked improvement; c. 50% improvement in appearance of hyperpigmentation
4	Slight improvement, some improvement (c. 25%); significant evidence of hyperpigmentation remains
5	No improvement; hyperpigmented condition unchanged
6	Worse; condition worse than at week 0

9. Statistical Methods of Analysis

[REDACTED]

[REDACTED]

[REDACTED]

[REDACTED]

The primary outcome of effectiveness will be a paired comparison of baseline to all applicable post-baseline time points for hyperpigmentation and melasma severity using data obtained from Vectra H2 3D imaging results.

A descriptive statistical summary will be provided for the VISIA, Vectra H2, and Physician's Global Assessment Scale. The descriptive statistical summary includes the number of observations (N), mean, median, and standard deviation (SD), minimum (MIN) and maximum (MAX) values at all applicable time points.

The following will be calculated and reported for each evaluation parameter at the applicable post-baseline time point(s):

$$\text{Percent Mean Change from Baseline} = \frac{(\text{Visit Mean Score} - \text{Baseline Mean Score}) \times 100}{\text{Baseline Mean Score}}$$

For each new measurement set we will conduct a repeated measures of analysis of variance to detect difference between sample distributions. If differences are detected, we will subsequently evaluate specific pairwise comparisons among the post treatment visit times using a paired T-test or Wilcoxon signed-rank tests. All statistical tests will have a significance level alpha =0.05. P-values will be reported to 3 decimal places (0.000).

10. Potential Risks

Blistering, burning, scaling and infection (Rare)

Bruising (Rare)

Transient edema and/or erythema (Common)

Skin roughness and/or peeling (Common)

Pigmentary changes (Rare)

Eye injury (Rare)

Scarring (Rare)

Allergic reaction (Rare)

Photography

11. Adverse Events

At each visit, the Investigator will question the subject about adverse events using an open-ended question. If a potential adverse event is reported by the subject or identified during examination, directed questioning and examination will be performed when appropriate. [REDACTED]

[REDACTED]
[REDACTED]

Photographs will be taken to document any AEs if possible.

[REDACTED]
[REDACTED]
[REDACTED]
[REDACTED]

12. Subject Safety and Data Monitoring

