3.2. Primary Endpoints

- Assessment of improvement in overall facial hyperpigmentation using quantitative measurements provided by VISIA and Vectra H2 3D analysis of photos obtained at Baseline, 1-Month and 3-Months post-treatment to evaluate the efficacy of f1927 treatments
 - Calculate percent change from baseline in visualization and numeric analysis of brown and red areas utilizing the Facial Skin Analysis on Canfield's Imaging Systems
- Clinician assessment of pigmentation improvement using the Physician's Global Assessment Scale

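### Sections 3.2 and 9 define the primary endpoint differently: instrument, variable and PGA status do not match.

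*Combined protocol and SAP*

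**What the plan says.** Section 3.2 (Primary Endpoints) has two items. The first is improvement in facial hyperpigmentation from "quantitative measurements provided by VISIA and Vectra H2 3D analysis of photos obtained at Baseline, 1-Month and 3-Months post-treatment", with the instruction "Calculate percent change from baseline in visualization and numeric analysis of brown and red areas". The second is "Clinician assessment of pigmentation improvement using the" PGA scale.

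Section 9 (Statistical Methods of Analysis) states: "The primary outcome of effectiveness will be a paired comparison of baseline to all applicable post-baseline time points" and continues "for hyperpigmentation and melasma severity using data obtained from Vectra H2 3D imaging results". VISIA and the PGA are named in Section 9 only where it says "A descriptive statistical summary will be provided for the VISIA, Vectra H2, and" the PGA. Section 9 also asks for a percent mean change from baseline for every evaluation parameter.

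On testing, Section 9 says "For each new measurement set we will conduct a repeated measures of analysis of variance". If that shows a difference, "we will subsequently evaluate specific pairwise comparisons among the post treatment visit times" by paired t-test or Wilcoxon signed-rank test, with every test at 0.05.

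**The concern.** A primary endpoint has to be the same wherever the plan defines it. Here one section names two imaging systems, two colour measures and a clinician rating as primary, and the other names one imaging system and a differently described variable. Whoever reports the trial could follow either section and claim to have followed the plan, and could make that choice after seeing the results. The study is uncontrolled, enrols up to 30 subjects (Section 3.1) and hypothesises a statistically significant improvement over baseline (Section 1), so which result counts as the primary one matters.

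Two smaller defects in Section 9 belong with this. The percent-change formula extends to a scale that has no baseline value. It is also unclear whether the primary comparison with baseline is made only after a significant ANOVA.

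**Working it through.** **1. The two definitions side by side**

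| Element | Section 3.2 | Section 9 |
|---|---|---|
| Instrument | VISIA and Vectra H2 | Vectra H2 only |
| Variable | Percent change in brown and red areas | Hyperpigmentation and melasma severity |
| PGA | Primary | Named only in the descriptive summary |
| Visits | 1 and 3 months | All applicable post-baseline times |

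The last row is not a conflict. The schedule in Section 7.1 has H2 3D and VISIA photography only at Screening and at Visits 4 and 5, so Section 9's post-baseline times for imaging are the same 1- and 3-month visits. The first three rows do conflict.

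**2. When the sections give opposite verdicts**

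Take one parameter per instrument, tested at both visits. Section 9 then rests on two results (Vectra at 1 and 3 months). Section 3.2 rests on four (the same two plus VISIA at 1 and 3 months).

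- If all results must be significant, Section 3.2 cannot be met unless Section 9 is. Conflict means that Section 9 is met and Section 3.2 is not.
- If any one suffices, Section 9 cannot be met unless Section 3.2 is. Conflict means that Section 3.2 is met and Section 9 is not.

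**3. How often, as an illustration**

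From the documents: at most 30 subjects, alpha 0.05, two post-baseline visits. Assumed, because the visible text gives no figure: two-sided tests, normally distributed change scores, the same true effect on both instruments and visits, instrument correlation 0.9 to 0.5, visit correlation 0.5. Red area and the PGA are left out. The effect is the mean change divided by the SD of change. Each cell is 100,000 simulated trials with paired t-tests. Each range runs from instrument correlation 0.9 to 0.5.

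| Effect (SD) | Power per test, n = 30 | Conflict, all must succeed | Conflict, any one suffices |
|---|---|---|---|
| 0.35 | 46% | 7-15% | 7-16% |
| 0.53 | 80% | 7-15% | 3-6% |
| 0.7 | 96% | 3-5% | under 1% |
| 1.0 | about 100% | about 0% | 0% |

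Thirty is a ceiling. With 20 analysed, and the effects in the same order, the conflict rates are 5-11%, 8-18%, 6-14% and 1-2% (all), and 8-18%, 6-13%, 2-4% and about 0% (any).

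**4. The percent-change formula and the PGA**

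The formula is (visit mean − baseline mean) × 100 / baseline mean. Section 7.1 schedules the PGA only at Visits 4 and 5, and Table 1 in Section 8.2 scores change since week 0. There is no baseline mean to subtract or divide by, so the formula cannot be computed for the PGA.

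**5. The ANOVA gate**

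Read literally, the follow-up tests compare the post-treatment visits with each other, while the primary outcome compares each visit with baseline. The text can mean that the baseline comparison stands alone, or that it is made only after a significant ANOVA. The visible wording does not settle which.

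**The case against.** The strongest reply is that Section 9 only says how the endpoint is analysed, and that the redacted lines just before the quoted sentence may set a hierarchy. That stands in part. Redacted text in Sections 3.1, 8.1, 8.2 and 9 may well name a parameter, a visit or a success rule, so their absence from the visible text is not counted as an omission. But the visible sentence itself says what the primary outcome will be, and a hidden line cannot make it agree with Section 3.2.

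A second reply is that the ANOVA for each measurement set may extend to VISIA. It may, but being tested does not make a measure primary.

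Four stronger readings are tempting, and the documents do not support them:

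- *That the sections also differ on visits.* The schedule shows the same two imaging visits for both. A split between visits therefore cannot set one section against the other. Vectra alone splits between its two visits in about 23% of simulated trials at 0.53 SD with 30 analysed, and that would remain if the sections matched word for word. Such splits are not part of the size of this problem.
- *That Section 9's paired comparison was meant to include the PGA and fails.* It is limited to Vectra data. Only the percent-change formula reaches the PGA, and the scale's lack of a baseline score is by design.
- *That the type I error rate is inflated.* That would follow only if any one significant result could count as success, which the documents do not say.
- *That the simulated rates estimate what will happen in this trial.* Effect size and correlations are assumed, and red area and the PGA are not modelled.

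**Conclusion.** The inconsistency is real, can be seen in the visible text and should be fixed. Sections 3.2 and 9 disagree on instrument, variable and PGA status, and agree on visits. This conclusion needs no calculation.

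Its consequence depends on the unknown effect size. Under the stated assumptions with 30 analysed, opposite verdicts are a modest but real risk for small to moderate effects, reaching about 15% or 16% at the lower instrument correlation, and are negligible at 1.0 SD. These figures also presuppose an all-or-any success rule that the visible text does not give.

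The percent-change formula and the ANOVA wording are lesser, separate defects. Nothing here shows that the trial is invalid.

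**What to change.** Before the data are analysed, put one identical primary definition in Sections 3.2 and 9: instrument, a parameter that the instrument actually outputs, and visit. The documents do not say that Vectra H2 reports brown area, so the sponsor needs to confirm the parameter first. Test it by one paired comparison with baseline that does not depend on the ANOVA, and label the remaining measures secondary.

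If the sponsor prefers to keep several primary measures, both sections should say whether all must succeed or how alpha is shared among them.

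In either case, exempt the PGA from the percent-change formula and say how it is summarised. If a redacted line already sets a hierarchy, repeat it in Section 3.2.

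The cost is wording in two sections, and every measurement stays. The downside is that fewer readouts can be called primary, or that a stricter success rule applies.

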7.1. Outline of Procedures

Procedures/ Time Points:	Visit 1	Visit 2	Visit 3	Visit 4	Visit 5
	Screening (-30 to 0 days)	Baseline/ Treatment #1* (Day 0 ; \pm 3 days)	Treatment #2 (Day 30; \pm 3 days)	1-month post-treatment (\pm 3 days)	3-months post-treatment (\pm 3 days)
Informed Consent	X				
Enrollment Paperwork	X				
Medical History/ Concomitant Medications	X	X	X	X	X
Pregnancy Test	X				
MOXI Treatment		X	X		
Standard Photography	X			X	X
H2 3D and VISIA Photography	X			X	X
Physician's Global Assessment Scale				X	X
Safety Assessment		X	X	X	X

* Treatment #1 (Visit 2) activities may be conducted at the Screening visit (Visit 1)

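### Section 9's percent-change formula has no visible exception for the Physician's Global Assessment, which has no baseline score to put into it

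*Combined protocol and SAP*

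**What the plan says.** Section 3.2 gives two primary endpoints. The first is imaging (VISIA and Vectra H2), with percent change from baseline as a sub-item. The second is "Clinician assessment of pigmentation improvement using the Physician's Global Assessment Scale", which has no such sub-item.

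The row for "Physician's Global Assessment Scale" in the Section 7.1 schedule is marked at Visit 4 (1 month) and Visit 5 (3 months) only. The imaging row is marked at Visit 1 as well.

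Table 1 in Section 8.2 runs from 0 (clear) to 6. Score 5 is "No improvement; hyperpigmented condition unchanged" and score 6 is "Worse; condition worse than at week 0". Scores 4, 3, 2 and 1 are labelled as roughly 25, 50, 75 and 90% improvement or clearance.

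Section 9 then makes four relevant statements:

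- The primary outcome: "The primary outcome of effectiveness will be a paired comparison of baseline to all applicable post-baseline time points", using Vectra H2 data.
- The summaries: "A descriptive statistical summary will be provided for the VISIA, Vectra H2, and Physician's Global Assessment Scale". They consist of N, mean, median, SD, minimum and maximum.
- The formula, which is the visit mean minus the baseline mean, times 100, divided by the baseline mean: "The following will be calculated and reported for each evaluation parameter at the applicable post-baseline time point(s").
- The testing: "For each new measurement set we will conduct a repeated measures of analysis of variance to detect difference between sample distributions". If a difference is found, paired tests between post-treatment visits follow. Alpha is 0.05 for all tests.

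Parts of Sections 8.2 and 9 are redacted.

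**The concern.** In the formula sentence, the word applicable limits the time points, not the parameters. The sentence follows directly on a paragraph that names the PGA as one of three measures, so on its face it covers the PGA. But the PGA has no baseline value, and its scale could not sensibly supply one: a score that rates change since week 0 cannot itself be rated at week 0.

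So a stated calculation cannot be carried out for an endpoint that Section 3.2 lists as primary. At analysis it would be left out without a stated rule, or filled with a baseline value chosen then.

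A second question is conditional. Section 9 does not visibly define a new measurement set. If that term includes the PGA, the repeated-measures ANOVA can compare only Visit 4 with Visit 5. That is a question about durability, not about improvement.

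**Working it through.** **1. Can the formula be computed?**

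| Measure | Scored before treatment (7.1) | Scored at Visits 4 and 5 | Baseline mean | Formula |
|---|---|---|---|---|
| VISIA | Yes, Visit 1 | Yes | Exists | Computable |
| Vectra H2 | Yes, Visit 1 | Yes | Exists | Computable |
| PGA | No | Yes | None | No value |

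The baseline mean stands in both the numerator and the denominator, so for the PGA nothing can be evaluated.

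**2. What if a baseline were supplied?** This is hypothetical; the plan does not call for it. With an assumed baseline b, the formula is (score − b) × 100 / b.

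| Score | Table 1 label, improvement | b = 5 | b = 6 |
|---|---|---|---|
| 4 | c. 25% | −20% | −33.3% |
| 3 | c. 50% | −40% | −50% |
| 2 | c. 75% | −60% | −66.7% |
| 1 | c. 90% | −80% | −83.3% |

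For example, score 3 with b = 5 gives (3 − 5) × 100 / 5 = −40%. With b = 0 the formula divides by zero. The result depends on the value chosen, and with b = 5 it is only a rescaled visit mean that does not match the scale's own percentages.

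**3. What can the ANOVA say, if it includes the PGA?** With two visits, F equals the square of the paired t for Visit 4 against Visit 5. If the score distribution is the same at both visits, its null hypothesis is true and it rejects in about 5% of trials by construction, however many subjects improved. No simulation is needed to show this.

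**4. What would a direct comparison with the unchanged category offer?** Take an exact two-sided sign test of improved (below 5) against worse (above 5), with scores of 5 as ties. Section 3.1 allows up to 30 subjects. The improved and worse shares are assumptions, as the documents give none.

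- Smallest significant count at 0.05: 21 of 30 untied (p = 0.043) or 15 of 20 (p = 0.041).
- Smallest significant count at 0.025: 22 of 30 (p = 0.016) or 16 of 20 (p = 0.012).

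Power is the sum, over the binomial number of untied subjects, of the chance that the improved count reaches the critical value:

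| Improved / worse (assumed) | n = 30, 0.05 per visit | n = 30, fixed 0.025 per visit | n = 24, fixed 0.025 per visit |
|---|---|---|---|
| 30% / 10% | 30.7% | 22.5% | 15.6% |
| 40% / 10% | 58.6% | 47.4% | 36.0% |
| 50% / 10% | 80.9% | 70.6% | 58.2% |
| 60% / 10% | 92.6% | 86.8% | 76.3% |
| 70% / 10% | 97.7% | 95.6% | 88.3% |

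The n = 24 column assumes 20% loss (30 × 0.8). At n = 30, a fixed split of alpha costs 58.6 − 47.4 = 11.2 points at 40% improved and 92.6 − 86.8 = 5.8 points at 60%. Holm would cost less, because once the smaller p-value passes 0.025 the larger is tested at 0.05.

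**5. Precision of the proportion improved.** Exact 95% intervals with 30 subjects are 31–69% for 15 improved, 47–83% for 20 and 61–92% for 24.

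**The case against.** The strongest reply is that the formula was never meant for the PGA. Section 3.2 is the only other place that mentions percent change, and it puts it under imaging alone. The term evaluation parameter is not defined, so an imaging-only reading is workable. This stands as a reading of intent. It does not settle the text, because Section 9 names the PGA one paragraph earlier and makes no visible exception. If imaging-only is meant, saying so is the repair.

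The second reply is that little depends on it. An analyst would leave the PGA cell empty, the planned median at each visit would still describe improvement, and the Vectra H2 outcome is untouched. This also stands, and it is why the point is minor.

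A reader might infer more: that the plan has no test of improvement on the PGA, or that its ANOVA would hide a real benefit. The documents do not support either. Parts of Sections 8.2 and 9 are redacted and may hold a PGA rule, and the visible text does not say whether the ANOVA includes the PGA. Comparing Visit 4 with Visit 5 is also a legitimate question in its own right. Setting its 5% rejection rate beside the sign test's power would contrast two different hypotheses.

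**Conclusion.** The point holds as a minor inconsistency. As worded, Section 9 asks for a percent change that has no value for the PGA at either visit. This rests on the visible schedule, Table 1 and formula, and on reading Section 9 as written; the narrower imaging-only reading remains possible.

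It does not show that the primary analysis fails. The imaging measures have a Visit 1 baseline, and the outcome Section 9 calls primary can be analysed as stated. Nor does it show that the complete plan lacks a PGA test. What can be said is that the visible text gives the PGA descriptive statistics and, at most, a comparison between the two follow-up visits. The power figures describe the suggested test under assumed response shares; they do not measure the defect.

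**What to change.** In Section 9:

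1. Limit the percent-change formula to VISIA and Vectra H2.
2. For the PGA, report at each of Visits 4 and 5 the score distribution, the median and the proportion improved (score below 5) with an exact 95% confidence interval, alongside the planned summary.
3. Unless redacted text already gives a PGA test, prespecify one comparison with the unchanged category, for example the exact two-sided sign test against 5. State how alpha is handled over the two visits: Holm, or the plan's 0.05 at each visit, declared as such. If redacted text holds a PGA rule, align the formula sentence with it.
4. If the repeated-measures ANOVA is meant to include the PGA, state that it compares Visit 4 with Visit 5 only and is not a test of improvement. It need not be dropped.

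The cost is a few sentences, with no new data, visits or subjects. The sign test ignores the size of improvement, and its power is modest if only about 40% improve, so the distribution and interval should carry much of the interpretation.

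### Does the percent-change formula have to state that both of its means come from the same subjects?

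*Combined protocol and SAP*

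**What the plan says.** The relevant text is in Section 9 (Statistical Methods of Analysis), which opens with four redacted blocks. The first visible sentence sets the effectiveness analysis: "The primary outcome of effectiveness will be a paired comparison of baseline to all applicable post-baseline time points", using Vectra H2 data. Next come descriptive summaries of VISIA, Vectra H2 and the Physician's Global Assessment, with N, mean, median, SD and range at each time point.

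The section then gives "Percent Mean Change from Baseline" for every evaluation parameter at each post-baseline visit:

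100 × (visit mean − baseline mean) / baseline mean.

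For testing, the section says that "we will conduct a repeated measures of analysis of variance to detect difference between sample distributions", followed by paired t-tests or Wilcoxon signed-rank tests.

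Section 3.2 places a percent change under the first primary endpoint: "Calculate percent change from baseline in visualization and numeric analysis of brown and red areas". The Section 9 formula is the only visible definition of such a quantity, so linking the two is an inference.

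In the Section 7.1 schedule, the "Physician's Global Assessment Scale" is marked only at the two post-treatment visits. Its score of 5 in Section 8.2 reads "No improvement; hyperpigmented condition unchanged", so the scale already rates change.

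**The concern.** The formula uses two group means and is not an average of within-subject changes. Because the preceding summaries carry their own N at each visit, a programmer could take the baseline mean over everyone enrolled and the visit mean over those who returned. The result would then mix treatment effect with a change in who is being averaged. If more heavily pigmented subjects leave, improvement is overstated; if less pigmented subjects leave, it is understated.

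The study is small and has no control arm, so readers are likely to judge the size of the effect from this percentage. It could also describe different people from the paired comparison beside it. Two smaller points go with this: no confidence interval is visible for the percentage, and the formula cannot be computed for the Physician's Global Assessment, which has no baseline mean.

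**Working it through.** The visible text gives no dropout rate, SD, expected change or computed percentage, so there is no planned figure to reproduce. The only input from the documents is the ceiling of 30 subjects (Section 3.1). All other inputs below are assumptions, with a higher score taken to mean more pigmentation.

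**Notation.** R is the true visit mean divided by the true baseline mean; k is the number lost; d is the relative distance of their mean baseline from the overall mean. The completers' baseline mean, relative to the overall mean, is m = (30 − k(1 + d)) / (30 − k).

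**Step 1: same ratio R in every subject.** Unmatched figure = R·m − 1; matched figure = R − 1.

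- R = 1, k = 3, d = +20%: m = 26.4/27 = 0.978, so unmatched is −2.2%; with d = −20% it is +2.2%.
- R = 1, k = 5, d = +30%: m = 23.5/25 = 0.94, so unmatched is −6.0%; with d = −30%, m = 1.06 and it is +6.0%.
- R = 0.8, k = 5: unmatched is 0.8 × 0.94 − 1 = −24.8%, or 0.8 × 1.06 − 1 = −15.2%. Matched is −20.0% in both.
- k = 0: m = 1, so the two versions agree exactly.

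**Step 2: loss unrelated to baseline.** The shift averages about zero, with SD = R × CV × √(1/(30 − k) − 1/30). At R = 1:

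- k = 1: 0.0339 × CV, which is 1.0 points (CV 0.3) to 1.7 points (CV 0.5).
- k = 3, CV 0.3: 0.0609 × 0.3 = 1.8 points.
- k = 5, CV 0.5: 0.0816 × 0.5 = 4.1 points.

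**Step 3: baseline and visit not perfectly correlated.** Step 1 makes matching look exact only because every subject has the same ratio. Let dropout depend on baseline alone, with linear regression, correlation ρ and visit SD equal to R times baseline SD. The completers' visit mean is then R(1 + ρ(m − 1)). With R = 0.8 and k = 5:

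| ρ | m | visit mean | unmatched | matched |
|---|---|---|---|---|
| 0.9 | 0.94 | 0.7568 | −24.3% | −19.5% |
| 0.9 | 1.06 | 0.8432 | −15.7% | −20.5% |
| 0.7 | 0.94 | 0.7664 | −23.4% | −18.5% |
| 0.7 | 1.06 | 0.8336 | −16.6% | −21.4% |

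Matching is closer to −20% throughout but does not recover it. At ρ = 0.7 the error falls from about 3.4 points to about 1.4 to 1.5, not to zero.

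**Step 4: the tests.** A paired t-test or signed-rank test uses within-subject differences. A subject with no value at a visit contributes none, so the choice of baseline mean in the descriptive formula cannot alter a p-value.

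**Step 5: precision.** For scale, with 25 matched pairs the approximate 95% half-width is 2.064 × R × CV × √(2(1 − ρ)/25). At R = 0.8 this is 4.4 points (CV 0.3, ρ 0.9) to 12.8 points (CV 0.5, ρ 0.7). The selective-loss shifts in Step 1 are of the same order as this uncertainty or smaller.

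**The case for a change.** The strongest case for acting is that the formula is introduced separately from the paired comparison, is written in group means, and could be followed to the letter with mismatched subjects. Selection need not be extreme to matter. In simulations with 20% dropout, an odds ratio of 2 for leaving per SD of baseline, and CV 0.2 to 0.5, a true change of −10% was reported on average as −12.3% to −15.9% unmatched, against −10.0% matched (the same ratio being assumed in every subject). A sentence would settle it at almost no cost.

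The algebra stands: the unmatched version is inferior whenever loss depends on baseline. What does not stand is the step from an unwritten definition to a defect. It needs three things together: appreciable loss, loss linked to baseline pigmentation, and an analyst who keeps absent subjects in the baseline mean. The documents point away from the first, since Section 7.5 expects every subject at both follow-up visits and exclusion 26 screens out likely non-completers. They give no evidence for the second. The paired setting of Section 9 makes the third unlikely. N at each time point would also show a reader where the numbers differ. Finally, the redacted blocks may contain the rule, and what is hidden by redaction cannot be counted as absent.

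**Conclusion.** No change to the plan is needed. The subject set for this descriptive percentage is not visible, but it is a detail that an analyst running paired tests and a repeated-measures analysis would fill sensibly by using the subjects with both values. Redacted text may already say so.

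Under the less natural reading, the shift is 2.2 to 6.0 points at no true change, on assumed selective losses of 3 to 5 of 30. It is zero with full follow-up and about zero on average with non-selective loss. Matching removes most of the shift at correlations of 0.7 to 0.9 but not all of it, and it does nothing about dropout related to response. No hypothesis test is affected.

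A confidence interval for the percentage and a stated set for the ANOVA would be reporting additions, not corrections. Naming the Physician's Global Assessment among the formula's parameters is a clerical slip: with no baseline score the percentage cannot be formed, and the scale's planned descriptive summary is unaffected.
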